4. STUDY ENDPOINTS

4.1. Primary Endpoints

- Proportion of participants experiencing Treatment Emergent Adverse Events (TEAE)s and severity of TEAEs
 - Number of participants who withdraw due to adverse events (AE)s
 - Change from baseline in vital signs, clinical laboratory parameters, Electrocardiograms (ECG)s, and Columbia Suicide Severity Rating Scale (C-SSRS) responses.

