8. STATISTICAL ANALYSIS

8.1. General Considerations

Continuous data will be summarized with the number of participants (n), mean, standard deviation (SD), minimum, and maximum. The minimum and maximum will be reported to the same number of decimal places as the raw data recorded in the database. The mean and median will be reported to one more decimal place, and the SD (and the standard error [SE], if applicable) will be reported to two more decimal places, than the raw data recorded in the database. In general, the maximum number of decimal places reported will be four for any summary statistic. Any values that require transformation to standard units (metric or SI) will be converted with the appropriate corresponding precision.

Categorical data will be summarized with the number of participants providing data at the relevant time point (n), frequency counts and percentages. Percentages will be reported to one decimal place unless otherwise specified. Any planned collapsing of categories will be detailed in the SAP text and the data displays.

Percentages will not be presented for zero counts. Percentages will be calculated using the number of participants (n) in the respective analysis set as the denominator. A missing category shall be included only for categorical variables where no data is available. The missing category will be omitted if there are no missing values for that variable.

For the laboratory results that are “ $\leq x$ ” or “ $\geq x$ ”, where x is a number as collected in the data, the numeric part of the result will be used in the calculation in the summary tables. If a laboratory value contains ‘y <’ then y minus 0.1 for values measured to the first decimal place, 0.01 for values measured to the second place, 0.001 for values measured to the third decimal place, and so on, will be used for the analysis. If a laboratory value contains ‘z >’ then z plus 0.1 for values measured to the first decimal place, 0.01 for values measured to the second place, 0.001 for values measured to the third decimal place, and so on, will be used for the analysis. The same is true if the result is presented as below limit of quantification (BLQ) and a lower limit of quantification (LLOQ) value is provided – LLOQ value will be used for calculation in the summary tables. The actual results as collected will be displayed in the listings.

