The analysis of AEs will be based on the concept of TEAEs. If the date of an adverse event is incomplete and an unambiguous determination could not be made with respect to its onset time versus the first dose of study drug and/or last dose of study drug, the adverse event will be assumed to be a TEAE. For imputation of missing AE dates, please refer to [Appendix B](#).

An overall summary of TEAEs will include the number and percentage of participants in the following categories:

- Any TEAEs
- Any TEAEs (Pre-treatment, On-treatment, Post-treatment)
- TEAEs by maximum Severity (severe>moderate>mild)
- Any TEAEs related to IP
- Any TEAEs leading to death
- Any TEAEs leading to IP discontinuation
- Any TEAEs leading to withdrawal from the study
- Any TEAEs leading to IP interruption
- Any serious TEAEs
- Any serious TEAE related to IP

- Any serious TEAE leading to IP discontinuation
- Any serious TEAE leading to withdrawal from the study

Incidence of TEAEs in following categories will be provided by System Organ Class (SOC) and Preferred Term (PT). A participant is counted only once under each SOC and PT in case of multiple occurrences of the same AE. These tables will be sorted by decreasing frequency of SOC in overall group, then alphabetically first within SOC then within PT.

- Any TEAE
- TEAEs by maximum severity
- TEAEs by relationship
- Serious TEAEs
- TEAEs leading to IP discontinuation
- TEAEs leading to withdrawal from the study
- TEAEs leading to IP interruption

Additionally, incidence of TEAEs will be summarized by PT. Most common TEAEs reported >5% in any cohort will also be summarized by PT.

For maximum severity, participants will be counted only once within each SOC and PT at the maximum severity in the following order: severe > moderate > mild; an AE with missing severity will be omitted from severity presentation and will not be imputed. For relationship to IP, participant will be counted only once within each SOC and PT at the strongest relationship to IP in the following order: related > not related; an AE with relationship missing is treated as related. For seriousness, an AE with missing seriousness will not be included in the summary tables. The incidences will be sorted by descending frequency of SOC and then, within a SOC, by descending frequency of PT based on overall group, and in alphabetical order of PT if the incidence within a PT is a tie.

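### SAP 8.3.1 omits adverse events with missing severity or seriousness and shows no missing count, so the severe and serious rows can only stay the same or fall

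*SAP*

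**What the plan says.** SAP 4.1 lists as a primary endpoint "Proportion of participants experiencing Treatment Emergent Adverse Events (TEAE)s and severity of TEAEs". SAP 8.3.1 then sets the rules for incomplete adverse event records:

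- **Severity:** "an AE with missing severity will be omitted from severity presentation and will not be imputed".
- **Relationship:** "an AE with relationship missing is treated as related".
- **Seriousness:** "an AE with missing seriousness will not be included in the summary tables".
- **Onset that cannot be placed relative to dosing:** "the adverse event will be assumed to be a TEAE".

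For the severity tables, "participants will be counted only once within each SOC and PT at the maximum severity in the following order: severe > moderate > mild". SAP 8.1 adds two general rules. On denominators: "Percentages will be calculated using the number of participants (n) in the respective analysis set as the denominator". On blanks: "A missing category shall be included only for categorical variables where no data is available"; the sentence after it drops that category when nothing is missing. Protocol 13.2 states that missing data will not be imputed. SAP 8.3.1 specifies no missing row, footnote or sensitivity count for severity or seriousness. It does list every TEAE by participant.

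**The concern.** Within one section, two kinds of missing information are resolved on the cautious side (relationship and onset date) and two are omitted (severity and seriousness). No reason is given for the difference.

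The omitted fields matter most here. Severity is named in a primary endpoint. Seriousness drives four rows of the overall TEAE summary and a separate table by system organ class and preferred term.

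The denominator does not shrink when a record is omitted, so any loss shows as a lower percentage and not as a smaller base. Because each participant is counted once at the maximum grade, an ungraded worst event does more than disappear: the participant is reported at whatever lower grade is left. With no missing row or footnote, a reader of the tables cannot see that either has happened.

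**Working it through.** The documents give no figure that depends on this rule, so there is nothing to reproduce. The check is of direction first, then of scale.

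**1. Direction, severity.** Take one participant with 1, 2 or 3 adverse events. Each event is mild, moderate or severe, and its grade is either recorded or missing, so each event has 6 states. The number of patterns is 6 + 6² + 6³ = 6 + 36 + 216 = 258. For each pattern, compare the true maximum grade with the maximum left after ungraded events are omitted.

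| Category | Patterns where the participant is added | Patterns where the participant is lost |
|---|---|---|
| Severe | 0 | 71 |
| Moderate | 26 | 25 |
| Mild | 34 | 3 |

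In 39 patterns every event is ungraded and the participant leaves the severity table. The table reconciles: losses 71 + 25 + 3 = 99, gains 26 + 34 = 60, and 99 − 60 = 39. These counts show what can happen, not how often.

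Three results follow:

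- The severe count never rises.
- The total with a graded TEAE never rises. The 39 patterns are those in which the severity rows would fall short of *Any TEAEs*, because the severity rule removes the event only from the severity presentation.
- Mild and moderate counts can move either way. For example, a participant with one mild event and one ungraded event that was in truth severe is shown as mild.

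**2. Direction, seriousness.** An unflagged event that was in truth serious is lost from the serious-TEAE rows, unless the participant has another flagged one. An unflagged event that was not serious costs those rows nothing. The serious-TEAE count is therefore lower or unchanged.

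**3. Scale per participant.** The actual Safety Set size is not given. SAP 6.1 says that Cohort 3 was not enrolled, so I use the rollover number planned in Protocol 13.8, 156, as an assumption. The change in a row for *m* affected participants is 100 × m / 156:

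- m = 1: 0.64 percentage points
- m = 2: 1.28
- m = 3: 1.92
- m = 5: 3.21

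The tables are also shown by cohort. Cohort columns have smaller denominators, so the step there would be larger.

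**4. Scale under assumed missing rates.** Let p be the true proportion with a serious TEAE and q the share of those whose flag is missing, with one serious event each. The table would show 100 × p × (1 − q). Neither p nor q is in the documents.

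| p | q = 1% | q = 10% |
|---|---|---|
| 5% | 4.95% | 4.50% |
| 15% | 14.85% | 13.50% |

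**The case against.** The case for leaving the SAP alone has four parts.

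**Omission follows the protocol.** Protocol 13.2 rules out imputation, so leaving severity and seriousness blank is the compliant choice and the relationship rule is the exception. This stands. It means the omission rule is not an error in itself, and that counting blanks as severe or serious should not become the main analysis. It does not argue against showing how many are blank: a missing row imputes nothing.

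**Blanks will be rare.** Protocol 12.2.5 has the investigator report intensity, causality and any applicable seriousness criteria for each event. Protocol 12.2.6 requires notification of serious events within 24 hours on a separate form. Protocol 14.1 has monitors verify source data and confirm that events are properly documented. This largely stands, and it is why the effect is probably small. But neither document says that the fields cannot be blank, and the SAP writes rules for when they are.

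**Nothing vanishes.** Every TEAE is listed by participant. That is true, although an event without a seriousness flag could be absent from the separate listing of serious events, and a listing does not correct a summary table.

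**The analysis is purely descriptive (SAP 2).** No test is affected. The counts are still the main safety output.

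A reader might also infer that an event with missing seriousness leaves every table, including *Any TEAEs*. The documents do not support this well. The sentence opens by restricting itself to seriousness and is the third of three parallel clauses, each governing its own presentation. The natural reading covers the serious-TEAE tables only. The reference to the summary tables is loose enough to deserve a clarifying sentence, but no loss from the any-TEAE endpoint is shown.

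**Conclusion.** The point holds as a cheap improvement. As written, the rule can only lower or leave unchanged three counts: participants with a severe TEAE, with any graded TEAE, and with a serious TEAE. It can also downgrade a participant whose worst event is ungraded, and the tables would not reveal it.

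The number affected cannot be derived from the documents and may be zero. The figure of about 0.64 percentage points per participant rests on a Safety Set of 156, which is a planned number. The percentages in the last table rest on assumed event and missing rates.

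Two further inferences should be avoided. It is not true that every severity count can only fall, since mild and moderate counts may rise. Nor do the documents say that events still open when the study was terminated are more likely to lack a grade or flag: an open event lacks an end date, but nothing indicates that it lacks severity or seriousness.

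**What to change.** In SAP 8.3.1:

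1. Replace the omission rule with a Missing row in the severity and serious-TEAE summaries. This agrees with the general provision for a missing category in SAP 8.1 and with Protocol 13.2. In the severity summary, the row would hold participants who have a TEAE but none with a grade, so that the rows add up to *Any TEAEs*.
2. Footnote the number of participants with any ungraded or unflagged TEAE. The row alone would not show participants who also have a graded event and may have been downgraded.
3. If any blanks remain at database lock, add a worst-case count (missing taken as severe, or as serious) as a supplementary line and not as the main rule.
4. State that the seriousness clause applies only to the serious-TEAE tables, and that no event leaves *Any TEAEs* because an attribute is missing.

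Querying blank severity and seriousness fields before lock may make the row and footnote unnecessary.

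The cost is a few sentences in the SAP and one extra row or footnote. The only downside is that counts could look slightly less favourable. If nothing is missing, the row drops out and the results do not change.

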8.3.2. Clinical Laboratory

Clinical laboratory assessments will include blood samples for hematology, clinical chemistry, coagulation, and urinalysis. Analytes to be evaluated are summarized in [Table 4](#).

All laboratory values will be summarized for the Safety Set by cohort and overall. Results of continuous hematology, clinical chemistry parameters, coagulation, and urinalysis parameters (quantitative) at each scheduled visit and mean changes from baseline will be summarized using standard international (SI) units. In addition, it will also include the summary of anytime on treatment, last values on treatment and last value on study.

All laboratory results will be listed in individual participant data listings.

Results from Hepatitis B and C screening tests, HIV-1 and -2 antibody, CAG test, FSH test at Screening will be listed separately by participant.

Results from urine drug test pregnancy test will be listed separately by participant.

Normal ranges for each parameter will be provided by the laboratory.

Table 4: Summary of Clinical Laboratory Analytes

Biochemistry	Renal Panel: glucose, calcium, phosphorus, blood urea nitrogen, creatinine, sodium, potassium, chloride, bicarbonate Hepatic Panel: albumin, alanine aminotransferase, alkaline phosphatase, aspartate aminotransferase, total bilirubin, direct bilirubin, indirect bilirubin, total protein, lactate dehydrogenase, gamma glutamyl transferase Other: triglycerides, cholesterol (low density lipoprotein [LDL], high density lipoprotein [HDL]), creatine phosphokinase, TSH and reflex to free T3/T4 if TSH is abnormal
Hematology	Red blood cell (RBC) count, hemoglobin, hematocrit, white blood cell count with differential, platelet count, RBC indices (mean corpuscular volume [MCV], mean corpuscular hemoglobin [MCH], and mean corpuscular hemoglobin concentration [MCHC]).
Urinalysis	Protein, glucose, pH, blood, leukocyte esterase, urobilinogen, bilirubin, ketones, nitrite
Coagulation	Activated partial thromboplastin time, prothrombin time, and international normalized ratio
Serology (screening only for Cohort 2 and 3)	Hepatitis B and C screening tests, HIV-1 and -2 antibody

Liver function tests will be monitored closely for potentially clinically significant PCS values, and will be summarized for occurrence anytime post-baseline for the following parameters for these PCS threshold (for condition involving more than one parameter, the results need to be from the same timepoint):

- Alanine Aminotransferase: >3xULN, >5xULN, >10xULN
- Aspartate Aminotransferase: >3xULN, >5xULN, >10xULN

- Alanine Aminotransferase or Aspartate Aminotransferase: $>3\times\text{ULN}$, $>5\times\text{ULN}$, $>10\times\text{ULN}$
- Alkaline Phosphatase: $>1.5\times\text{ULN}$, $>2\times\text{ULN}$
- Total Bilirubin: $>1.5\times\text{ULN}$, $>2\times\text{ULN}$
- Total Bilirubin $>2\times\text{ULN}$ **AND** (Alanine Aminotransferase or Aspartate Aminotransferase $>3\times\text{ULN}$) [any time post-baseline, does not need to be measured at the same time point of assessment]
- Total Bilirubin $>2\times\text{ULN}$ **AND** Alkaline Phosphatase $<2\times\text{ULN}$ (any time post-baseline, measured at the same time point of assessment) **AND** [(ALT or AST $>3\times\text{ULN}$) **AND** Alkaline Phosphatase $<2\times\text{ULN}$, any time post-baseline, measured at the same time point of assessment]

Note: The conditions in the first pair of brackets do not need to occur at the same timepoint as the conditions in the second pair of brackets.

8.3.3. 12-Lead Electrocardiogram

A single ECG will be measured after the participant has been in the supine position for at least 5 minutes. A summary of raw values and change from baseline values using the derived mean will be summarized by each scheduled visit for the following ECG parameters: heart rate, PR, QRS, QT, and QTcF interval. This summary will also include any value on treatment, last values on treatment and on study. A by-participant listing of 12-lead ECG will also be provided for each of the ECG measurements.

Each ECG is evaluated as ‘normal’, ‘abnormal, not clinically significant’ and ‘abnormal, clinically significant’. The number and percentage of participants with the categories of ‘abnormal, clinically significant’ and ‘abnormal, not clinically significant’ from the latest ECG value will be provided at baseline and each post-baseline scheduled assessment time point.

8.3.4. Vital Signs

Vital signs will include oral temperature($^{\circ}\text{C}$), respiratory rate (breaths per minute), heart rate (beats per minute [bpm]), and blood pressures (mmHg). Heart rate and blood pressure were collected in supine position and standing position at all scheduled time points.

Vital sign results and mean changes from baseline will be summarized by scheduled visit. It will also include the summary of last values on treatment and on study assessments.

8.3.5. Physical Examination

Only the physical examination dates and times are collected. These will be presented in individual participant data listings only. After screening, any clinically significant abnormal findings in physical examinations will be reported as AEs.

8.3.6. Columbia Suicide Severity Rating Scale

Suicidality data collected on the C-SSRS is collected during the study. The C-SSRS includes ‘yes’ or ‘no’ responses for assessment of suicidal ideation and behavior as well as numeric ratings for severity of ideation, if present (from 1 to 5, with 5 being the most severe).

The participant’s non-suicidal self-injurious behaviors is also assessed separately as part of C-SSRS.

The “Baseline/Screening” C-SSRS form will be completed at screening (lifetime history). The “Since Last Visit” C-SSRS form will be completed at all subsequent time points.

The assessments for suicidal ideation are ranked as follows with 5 being the worst:

1. Wish to be dead
2. Non-specific active suicidal thoughts
3. Active suicidal ideation with any methods
4. Active suicidal ideation with some intent
5. Active suicidal ideation with specific plan

The assessments for suicidal behavior are ranked as follows with 5 being the worst:

1. Preparatory acts or behavior
2. Aborted attempt
3. Interrupted attempt
4. Actual attempt (non-fatal)
5. Completed suicide

Suicidal behavior is considered worse than suicidal ideation.

Baseline for each question is defined as the worst of the assessments done before the first dose of IP, excluding the lifetime version. This will typically include the ‘past 12-month’ version from screening and ‘since last visit version’ from Day 1, as well as any unscheduled visits done before the first dose of IP; any Yes will make the baseline value as Yes.

The number and percentage of participants with at least one response of ‘Yes’ to any C-SSRS suicidal ideation or suicidal behavior item, as well as for Participant’s non-suicidal self-injurious behavior, will be summarized first by visit, then separately for baseline and anytime post-baseline.

Summary of shift from baseline in C-SSRS suicidal ideation and suicidal behavior will be presented for the following categories (no suicidal ideation/behavior, suicidal ideation, and suicidal behavior) for each scheduled assessment time point. If the answer to the first and second assessments in suicidal ideation and all non-missing assessments in suicidal behavior is ‘No’, then the category for the table is considered as ‘No suicidal ideation/behavior’. If any of the assessments in suicidal behavior is Yes, the category is considered as ‘Suicidal behavior’. If any of the assessments in suicidal ideation is Yes but all assessments in suicidal

behavior is No, the category is considered as 'Suicidal ideation'. If the participant has both suicidal ideation as well as suicidal behavior, the participant will be counted under suicidal behavior only.

In addition, a summary of shift in suicidal ideation from baseline maximum rank score for any time post-baseline maximum rank score will be presented. Maximum score 0 refers to all 'No' for all assessments in the desired period for all 5 questions on suicidal ideation.

A bar graph for percentage of participants with suicidal ideation and suicidal attempt over time will be provided.

A listing of suicidal ideation and suicidal behavior will be provided.

8.4. Other Analysis

Not applicable

9. SUMMARY OF INTERIM AND DMC ANALYSES

Not applicable

10. REFERENCES

11. LIST OF APPENDICES

APPENDIX A. SCHEDULE OF ASSESSMENTS

Table 5: Schedule of Assessments: De Novo (Cohort 3) and 718-CIH-201/202 >7 Day Gap Rollover (Cohort 2) Participants

Assessments	Screening Period Days -28 to -1	Treatment Period						
		Day 1	Day 30 (±7 days)	Day 60 (±7 days)	Day 90 (±7 days)	Day 180 (±14 days)	Day 270 (±14 days)	Day 365 (±14 days) ^b
Informed consent ^a	X							
Inclusion/exclusion criteria	X	X						
Family history and demographics	X							
Medical history ^c	X							
Participant training ^d	X							
Body weight	X	X				X		X
Body height ^e	X							
Vital signs (including orthostatics) ^f	X	X	X	X	X	X	X	X
Physical examination ^g	X	X	X	X	X	X	X	X
CAG test ^e	X							
FSH test ^h	X							
Serology test ⁱ	X							
12-lead ECG ^j	X	X	X		X	X		X
Safety laboratory assessments ^k	X	X	X		X	X	X	X
Urine drug test	X	X	X	X	X	X		X
Alcohol breath test	X	X	X	X	X	X		X
Cigarette/tobacco use assessment	X	X	X	X	X	X		X
Pregnancy test ^l	X	X	X		X	X	X	X

Assessments	Screening Period	Treatment Period						
		Day 1	Day 30 (± 7 days)	Day 60 (± 7 days)	Day 90 (± 7 days)	Day 180 (± 14 days)	Day 270 (± 14 days)	Day 365 (± 14 days) ^b
C-SSRS (Screening/Baseline) ^p	X (Cohort 3 only)							
C-SSRS (Since Last Visit) ^p	X (Cohort 2 only)	X	X	X	X	X	X	X
UHDRS ^q	X							
MoCA	X							

Assessments	Screening Period	Treatment Period						
	Days -28 to -1	Day 1	Day 30 (±7 days)	Day 60 (±7 days)	Day 90 (±7 days)	Day 180 (±14 days)	Day 270 (±14 days)	Day 365 (±14 days) ^b
IP self-administration ^w					X (once daily in the morning)			
IP dispensation ^x		X	X	X	X	X	X	X
IP accountability/return ^y			X	X	X	X	X	X
IP adherence monitoring					X			
AEs/SAEs ^z					X			
Prior and concomitant medications and procedures/therapies ^{aa}					X			

Abbreviations: AE = adverse event, CAG = cytosine-adenine-guanine trinucleotide repeat within the huntingtin gene, [REDACTED]; COVID-19 = coronavirus disease 2019; C-SSRS = Columbia–Suicide Severity Rating Scale; ECG = electrocardiogram; eCRF = electronic Case Report Form, FSH = follicle-stimulating hormone; [REDACTED]; HD = Huntington's Disease; [REDACTED]

[REDACTED] : HIV = human immunodeficiency virus; IP = investigational product; MoCA = Montreal Cognitive Assessment; [REDACTED] : SAE = serious adverse event; [REDACTED]

UHDRS =

Unified Huntington's Disease Rating Scale; [REDACTED]

NOTE: Any additional parent study data needed to support the 718-CIH-301 data or analyses will be carried over from the applicable parent study.

- ^a Both participants and study partners (if applicable) will be consented during the Screening Period. For gap rollovers only, a legally authorized representative may consent on behalf of participants who are not capable of providing informed consent in the opinion of the investigator.
- ^b Participants who have completed their Day 395 visit under Protocol Version 2 and wish to continue participation under Protocol Version 3 or higher (“718-CIH-301 v2 Completers”) will return to the site for a Re-Qualification visit (Table 7) up to 28 days prior to resuming IP at their Next Scheduled Study Treatment Visit (relative to the date of their Day 1 visit, see Table 8).
- ^c Includes full medical history carried over from the parent study for gap rollover participants. Any medical history from the end of the parent study through informed consent for 718-CIH-301 and any resolved AEs from parent study, if clinically relevant, will be recorded as medical history in the eCRF. For de novo participants, full medical history will be collected.
- ^d Participants and study partners (if applicable) will be trained by study staff on the use of software applications, devices, and diaries necessary for the conduct of the study. For the rollover participants, training can be customized based on participant's comfort level.

- e For De Novo (Cohort 3) only. For gap rollover participants (Cohort 2), these tests will be carried over from the corresponding parent studies, 718-CIH-201 or 718-CIH-202.
 - f Vital signs include body temperature, respiratory rate, heart rate, and blood pressure. On dosing days, vital signs will be measured prior to dosing. Blood pressure and heart rate will be measured after the participant has been in the supine position for at least 5 minutes and then repeated approximately 1 and 3 minutes after standing at all scheduled time points. Vital signs can be repeated once per visit if out of range.
 - g A full physical and neurological examination is to be conducted during Screening and on Day 180. At other visits, physical examinations will include a brief assessment of general appearance, cardiovascular, respiratory, gastrointestinal, and neurological systems and followed by a targeted physical assessment as needed. A symptom-directed examination may be conducted at any time at the discretion of the investigator.
 - h Serum FSH test will be conducted at Screening for the de novo female participants and rollover participants who are not surgically sterile and who have ≥ 12 months of spontaneous amenorrhea to confirm postmenopausal state as defined in this protocol. For the postmenopausal rollover participants (where postmenopausal state was confirmed in parent studies), the preceding results will be carried over from the corresponding parent studies, 718-CIH-201/202, as applicable.
 - i To include hepatitis B and C screening tests, HIV-1 and -2 antibody.
 - j A single ECG will be measured after the participant has been in the supine position for at least 5 minutes.
 - k Safety laboratory assessments will include blood samples for hematology, biochemistry, coagulation, and urine samples for urinalysis. On dosing days, samples will be collected ≤ 2 hours prior to dosing.
 - l Serum pregnancy tests will be conducted for all female participants at Screening. Urine pregnancy tests will be conducted at other scheduled time points for female participants that are not postmenopausal or surgically sterile.
 - ■ ■
 - o Only applicable for gap rollover participants that did not provide a genetic research sample in the parent study and for de novo participants.
 - p For gap rollover participants (Cohort 2), the C-SSRS (Since Last Visit) will be completed during Screening. For de-novo participants (Cohort 3), the C-SSRS (Screening/Baseline) will be completed at Screening. Participants in Cohort 2 and 3 will complete the C-SSRS (Since Last Visit) at all subsequent time points.

- x Study staff will dispense sufficient IP for the participant to take daily at home until the next scheduled visit.
- y Participants will bring all used packaging and unused IP to the clinic at each visit for study staff to review and document.
- z AEs/SAEs will be collected beginning with completion of 718-CIH-301 informed consent through end of study participation. For gap rollover participants, documented ongoing AE/SAE from the parent studies will be collected to follow through resolution.
- aa All medications, supplements, procedures, and therapies taken within 8 weeks prior to obtaining 718-CIH-301 informed consent will be recorded through the end of the study. All medications, supplements, procedures, and therapies used to treat Huntington's Disease or to treat or prevent COVID, regardless of timing will be recorded through the end of the 718-CIH-301 study.

Table 6: Schedule of Assessments: 718-CIH-201/202 Direct (≤ 7 days) Rollover (Cohort 1) Participants

Assessments	Carry-over Results of the Last Assessments from Parent Studies when Applicable ^{a,f}	Treatment Period						
		Day 1	Day 30 (± 7 days)	Day 60 (± 7 days)	Day 90 (± 7 days)	Day 180 (± 14 days)	Day 270 (± 14 days)	Day 365 (± 14 days) ^b
Informed consent ^c		X						
Inclusion/exclusion criteria		X						
Family history and demographics	X							
Medical history ^d	X	X						
Participant training ^e		X						
Body weight		X ^f				X		X
Body height	X							
Vital signs (including orthostatics) ^g		X ^f	X	X	X	X	X	X
Physical examination ^h	X		X	X	X	X	X	X
CAG test	X							
FSH test	X							
Serology test ⁱ	X							
12-lead ECG ^j	X		X		X	X		X
Safety laboratory assessments ^k	X		X		X	X	X	X
Urine drug test		X ^f	X	X	X	X		X
Alcohol breath test		X ^f	X	X	X	X		X
Cigarette/tobacco use assessment		X ^f	X	X	X	X		X
Pregnancy test ^l	X		X		X	X	X	X

Assessments	Carry-over Results of the Last Assessments from Parent Studies when Applicable ^{a,f}	Treatment Period						
		Day 1	Day 30 (±7 days)	Day 60 (±7 days)	Day 90 (±7 days)	Day 180 (±14 days)	Day 270 (±14 days)	Day 365 (±14 days) ^b
C-SSRS (Since Last Visit)	X		X	X	X	X	X	X
UHDRSP ^p	X							
MoCA	X							
IP self-administration ^w					X (once daily in the morning)			
IP dispensation ^x		X	X	X	X	X	X	X
IP accountability/return ^y			X	X	X	X	X	X
IP adherence monitoring					X			
AEs/SAEs ^z					X			

Assessments	Carry-over Results of the Last Assessments from Parent Studies when Applicable ^{a,f}	Treatment Period					
		Day 1	Day 30 (±7 days)	Day 60 (±7 days)	Day 90 (±7 days)	Day 180 (±14 days)	Day 270 (±14 days)
Prior and concomitant medications and procedures/therapies ^{aa}				X			

Abbreviations: AE = adverse event, CAG = cytosine-adenine-guanine trinucleotide repeat within the huntingtin gene, [REDACTED]; COVID-19 = coronavirus disease 2019; C-SSRS = Columbia–Suicide Severity Rating Scale; ECG = electrocardiogram; eCRF = electronic Case Report Form, FSH = follicle-stimulating hormone; [REDACTED]; HD = Huntington's Disease; [REDACTED]

[REDACTED]; HIV = human immunodeficiency virus; IP = investigational product; MoCA = Montreal Cognitive Assessment; [REDACTED]; [REDACTED]; SAE = serious adverse event; [REDACTED] erity; UHDRS =

Unified Huntington's Disease Rating Scale; [REDACTED].

NOTE: Any additional parent study data needed to support the 718-CIH-301 data or analyses will be carried over from the applicable parent study.

^a The carryover assessments constitute the baseline/screening assessments for this extension study.

^b Participants who have completed their Day 395 visit under Protocol Version 2 and wish to continue participation under Protocol Version 3 or higher ("718-CIH-301 v2 Completers") will return to the site for a Re-Qualification Visit (Table 7) up to 28 days prior to resuming IP at their Next Scheduled Study Treatment Visit (relative to the date of their Day 1 visit, see Table 8).

^c Both participants and study partners (if applicable) will be consented on Day 1. A legally authorized representative may consent on behalf of participants who are not capable of providing informed consent in the opinion of the investigator. [REDACTED]

^d Includes full medical history carried over from the parent study. On Day 1, any medical history from the end of the parent study through informed consent for 718-CIH-301 and any resolved AEs from parent study, if clinically relevant, will be recorded as medical history in the eCRF.

^e Participants and study partners (if applicable) will be re-trained, if needed be based on participant's comfort level, by study staff on the use of software applications, devices, and diaries necessary for the conduct of the study.

^f Participants completing the final visit day of the parent study (Day 112 in CIH-201 or Day 42 in CIH-202) and Day 1 of this study at the same clinic visit are not required to repeat testing for body weight, vital signs (unless they had supine vital signs outside of the ranges specified in exclusion criterion #8), urine drug test, alcohol breath test, and cigarette/tobacco use assessment twice.

^g Vital signs include body temperature, respiratory rate, heart rate, and blood pressure. On dosing days, vital signs will be measured prior to dosing. Blood pressure and heart rate will be measured after the participant has been in the supine position for at least 5 minutes and then repeated approximately 1 and 3 minutes after standing at all scheduled time points. Vital signs can be repeated once per visit if out of range.

- h The final physical and neurological examinations will be carried over from the parent study and will serve as Day 1 assessments in the current study. A full physical and neurological examination is to be conducted on Day 180. At other visits, physical examinations will include a brief assessment of general appearance, cardiovascular, respiratory, gastrointestinal, and neurological systems and followed by a targeted physical assessment as needed. A symptom-directed examination may be conducted at any time at the discretion of the investigator.
- i To include hepatitis B and C screening tests, HIV-1 and -2 antibody.
- j A single ECG will be measured after the participant has been in the supine position for at least 5 minutes.
- k Safety laboratory assessments will include blood samples for hematology, biochemistry, coagulation, and urine samples for urinalysis. On dosing days, samples will be collected \leq 2 hours prior to dosing.
- l Urine pregnancy tests will be conducted at scheduled time points for female participants that are not postmenopausal or surgically sterile.
- m [REDACTED]
- n [REDACTED]
- o Only applicable for direct rollover participants that did not provide sample(s) in the parent study.
- p [REDACTED]
- q [REDACTED]
- r [REDACTED]
- s [REDACTED]
- t [REDACTED]
- u [REDACTED]
- w At scheduled clinic visits, participants will self-administer IP in the clinic under the supervision of study staff. All scheduled safety assessments will be conducted prior to dosing. [REDACTED] will be administered post dosing. (All Day 1 assessments should be done predose).
- x Study staff will dispense sufficient IP for the participant to take daily at home until the next scheduled visit.
- y Participants will bring all used packaging and unused IP to the clinic at each visit for study staff to review and document.
- z AEs/SAEs will be collected beginning with completion of 718-CIH-301 informed consent through end of study participation. Documented ongoing AE/SAE from parent studies will be collected to follow through resolution.
- aa All medications, supplements, procedures, and therapies taken within 8 weeks prior to obtaining 718-CIH-301 informed consent will be recorded through the end of the study. All medications, supplements, procedures, and therapies used to treat Huntington's Disease or to treat or prevent COVID, regardless of timing will be recorded through the end of the 718-CIH-301 study.

Table 7: Schedule of Assessments: Additional Visits for 718-CIH-301 v2 Completers

Assessments	Re-Qualification Visit ^{a, b}	Next Scheduled Study Treatment Visit (See Table 8) ^c	Post Re-Qualification Safety Check-in
	Up to 28 days prior to Next Scheduled Study Treatment Visit		
Informed re-consent ^d	X		
Reconfirm inclusion/exclusion criteria ^e	X		
Interim medical history ^f	X		
Optional participant training ^g	X		
Body weight	X		
Body height	X		
Vital signs (including orthostatics) ^h	X		X
Physical examination ⁱ	X		X
Serology test ^j	X		
12-lead ECG ^k	X		X
Safety laboratory assessments ^l	X		X
Urine drug test	X		
Alcohol breath test	X		
Cigarette/tobacco use assessment	X		
Pregnancy test ^m	X		
<hr/>			
C-SSRS (Since Last Visit)	X		X
IP self-administration ⁿ			X
IP adherence monitoring			X
AEs/SAEs ^o	X		X
Prior and concomitant medications and procedures/therapies ^p	X		X

Abbreviations: AE = adverse event; C-SSRS = Columbia–Suicide Severity Rating Scale; ECG = electrocardiogram; eCRF = electronic Case Report Form; HIV = human immunodeficiency virus; IP = investigational product; SAE = serious adverse event.

- a Participants who have completed their Day 395 visit under Protocol Version 2 and wish to continue participation under Protocol Version 3 or higher (“718-CIH-301 v2 Completers”) will return to the site for a Re-Qualification Visit ([Table 7](#)) up to 28 days prior to resuming IP at their Next Scheduled Study Treatment Visit (relative to the date of their Day 1 visit, see [Table 8](#)).
- b Participants who have NOT completed their Day 395 visit under Protocol Version 2 but have completed their Day 365 visit and wish to continue participation under Protocol Version 3 or higher will NOT return to the site for a Re-Qualification Visit. They will return to the site for a Study Continuation Visit (Study Protocol, Appendix 2, Section 20.2) and then continue on to their Month 15 visit (see [Table 8](#)). The participant’s visit schedule should remain relative to the date of their Day 1 visit.
